7.6.1 Primary Efficacy Analysis

[figure not shown]
There are two co-primary efficacy endpoints. The first co-primary endpoint is change in 6-MWD from baseline at 18 months after randomization. The second co-primary endpoint is percent reduction in serum TTR burden over 18 months after randomization.

Efficacy of revusiran will be established if the p-value (2-sided) is \leq 0.05 for the primary analysis for each of the co-primary endpoints.

7.6.1.1 Change from Baseline in 6-MWD at Month 18

The primary analysis for change from baseline in 6-MWD at month 18 will be performed using a stratified Finkelstein and Schoenfeld Joint Rank Test.

This test will take into account informative missing-ness due to death or loss of ability to perform 6-MWD up to Month 18. In this stratified non-parametric rank sum analysis, all pairs of patients within a stratum are compared. A patient will be compared with another patient in a step-wise fashion to identify the patient in the pair with the better outcome:

7.6.1.2 Sensitivity Analyses for Change in 6-MWD from Baseline at Month 18

All sensitivity analyses will be analyzed using the mITT population.

Sensitivity #1: Address robustness using a different distributional assumption

A mixed-effects model repeated measures (MMRM) analysis based on the restricted maximum likelihood (REML) method for estimation will be performed for the change in 6-MWD from baseline. The MMRM model dependent variable will be change in 6-MWD from baseline (meters). The model will include the	
fixed effects of treatment group, visit, treatment group-by-visit interaction term, TTR mutation	
and 6-MWD at Screening and baseline 6-MWD-by-visit	
interaction. An unstructured covariance variance matrix will be used to model the correlation among	
repeated measurements. The Kenward-Roger approximation will be used to estimate the denominator	
degrees of freedom. The adjusted mean change in 6-MWD from baseline to each visit for each treatmen	t
group and corresponding 95% confidence interval will be displayed. The difference in the adjusted mean	n
change in 6-MWD between treatment groups at each visit and corresponding 95% confidence interval w	/ill
also be estimated. All post-baseline observations collected and designated to each post-baseline analysis	}
visit will be used in the analysis, including data collected after the discontinuation of study drug. Note the	nat
this analysis assumes missing data, including those due to death, are MAR.	

Sensitivity #2: Address influence of missing data

Complete Cases (CC) analysis will include all patients with non-missing 6-MWD results at 18 months. An ANCOVA model will be employed where the dependent variable is a change from baseline in 6MWD (meters) to month 18 with a covariate for treatment group. No imputation will be considered.

Below are additional descriptive analyses of each component of the co-primary analysis. These analyses will be unstratifed using the mITT population.

Time to death: The distribution of time from date of first dose of study drug to death for each treatment group will be generated using Kaplan-Meier (KM) plot. For each percentile (25th, 50th, 75th) if reached, an estimate of time of death from date of first dose and the associated 95% confidence intervals using Brookmeyer-Crowley methodology will be presented for each treatment group. The survival rates at 3, 6, 9, 12, 15 and 18 months for each treatment group will also be presented. Appendix I includes additional details regarding the definition for time to death.

Time to loss of ability to perform 6-MWD: Time from date of first dose to loss of ability to perform 6-MWD will be based on months 3, 6, 12 and 18 visits. The frequency and percentage of patients who lose the ability to walk will be presented at each analysis visit by treatment group. The cumulative number of patients and associated percentage in each treatment group who were unable to perform the 6-MWD up to month 18 will also be presented. In addition, there will also be a summary table and listing (overall and by visit) of the number (frequency) of patients that were unable to walk at the visit and the corresponding

Version: 1.0

Alnylam Protocol No. ALN-TTRSC-004

reasons why the patient was unable to walk. Appendix I includes additional details regarding definition of time to loss of ability to perform 6-MWD.

Change in 6-MWD from baseline: Descriptive statistics of observed change in 6-MWD (meters) from baseline to analysis visits at 3, 6, 12 and 18 months will be generated. Appendix I includes additional details regarding the definition of change in 6-MWD from baseline.

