6 DATA HANDLING

6.1 Time Points and Visit Windows

Day 1 will be defined as the day of first dose of study drug.

An evaluation date will be calculated relative to Day1 as follows:

- RelDay = (date of assessment date of first dose + 1) if collected after Day 1.
- RelDay = (date of assessment date of first dose) if collected prior to Day 1.

For analysis by visit, analysis windowing will be utilized for each scheduled visit such that unscheduled visits will also be considered. If there is more than one value within a visit window then the visit closest to the target day of the visit will be used in the analysis. If measurements are equally distant to the target day, then the later one will be used in the analysis. Details regarding the definition of the visit window will be summarized in a separate specifications document.

Baseline Definitions:

- For 6-MWD, baseline will be defined as the latest value prior to the first dose. If Day 1 assessment is not available, then the latest of the 2 screening 6MWD results will be selected to represent the baseline value for the patient in the analysis.
- For each of the PD parameters, baseline will be defined as the average of all measurements collected prior to the date of the first dose of study drug.
- For all other parameters, the baseline will be defined as the last assessment prior to the first dose
 of study drug.

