7.6 Efficacy

All efficacy analyses will be performed on the mITT population. In addition, the analysis of the coprimary efficacy endpoints will be also be evaluated using the PP population.

Where appropriate, analyses will be stratified based upon a subset of stratification parameters used for randomization: TTR mutation (V122I versus other FAC mutations), and 6-MWD (≤325 meters versus >325 meters). The values of these stratified parameters will be based upon the data entered in the eCRF.

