7.6.1.3 Percent reduction in serum TTR from Baseline over 18 months

The primary analysis for the co-primary endpoint of percent change in TTR from baseline over 18 months will be analyzed using an Analysis of Covariance (ANCOVA) model.

The dependent variable used in the ANCOVA model w	rill be area under the effect curve (eAUC) to			
quantify the percent reduction in TTR from baseline over 18 months. The covariates used in the model				
will be treatment group, TTR mutation	and 6-MWD at Screening			
and baseline TTR serum levels. The	difference in the adjusted mean eAUC between			
treatment groups will also be presented with associated 95% confidence interval. The dependent variable				
will be log transformed.	-			

Calculation of eAUC will be based on trapezoidal method, where the y-axis is percent reduction in serum TTR and the x-axis is time since first dose of study drug. Assessments missing due to death or discontinuation will be imputed using the baseline value, and thus the percent change will be 0%. The span of time will start at time 0 (baseline) and end at month 18. Only scheduled visits will be included in the calculation of eAUC.

7.6.1.4 Sensitivity Analyses for Percent Reduction in Serum TTR from Baseline over 18 months

Sensitivity #1: Address impact of baseline factors

The eAUC will be analyzed using an unadjusted ANOVA model. The covariates of the model will be treatment group and the dependent variable will be eAUC.

Sensitivity #2: Address robustness using a different distributional assumptions

A mixed-effects model repeated	l measures (MMRM) ana	alysis based on the re	stricted maximum likelihood
(REML) method for estimation w	vill be performed for rela	tive fold change in s	serum TTR. The dependent
variable will be relative fold cha	ange defined as (TTR va	lue at follow-up visi	t/baseline TTR value). The
covariates used in the model wil	ll be treatment group, vis	sit, treatment group b	by visit interaction, TTR
mutation	and 6-MWD at Screeni	ng	and baseline
TTR serum levels. The difference	ce in the adjusted mean i	relative fold change	n serum TTR between
treatment groups and associated	95% will also be presen	ited. The dependent	variable will be log
transformed.			

Sensitivity #3: Address influence of missing data

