Complete Cases (CC) analysis will include all patients with non-missing TTR results at month 18. The mixed-effect model used in the sensitivity #2 will be employed. No imputation will be considered. The dependent variable will be log transformed.

Below are additional descriptive analyses of serum TTR. These analyses will be unstratifed using the mITT population.

Serum TTR: Descriptive statistics of serum TTR values, change from baseline in serum TTR values and percent reduction in TTR values will be presented for each treatment group. An additional summary table of descriptive statistics for the maximum percentage reduction in TTR for each treatment group will also be presented.

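### The complete-case ANCOVA of 6-MWD change names treatment as its only term, so it differs from the MMRM in covariates as well as in missing-data handling

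*SAP*

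**What the plan says.** SAP 7.6.1.2 gives two sensitivity analyses for the 6-MWD co-primary endpoint.

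- **Sensitivity #1** is an MMRM. Besides treatment, visit and their interaction, it names TTR mutation "and 6-MWD at Screening and baseline 6-MWD-by-visit" interaction. It reports the adjusted treatment difference with a 95% CI at each visit.
- **Sensitivity #2** is headed "Sensitivity #2: Address influence of missing data". Its analysis set is stated as "Complete Cases (CC) analysis will include all patients with non-missing 6-MWD results at 18 months". The model is an ANCOVA of change "to month 18 with a covariate for treatment group. No imputation will be considered". The sentence has no gap where a blacked-out covariate could sit, whereas the MMRM sentence does have gaps.

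Three other places bear on how to read this:

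- In SAP 7.6.1.4 the complete-case analysis of serum TTR reuses a covariate-adjusted model: "mixed-effect model used in the sensitivity #2 will be employed". That model includes TTR mutation, screening 6-MWD and baseline TTR.
- In the same section, where no adjustment is wanted, the SAP says so and gives the purpose, which is to examine baseline factors: "The eAUC will be analyzed using an unadjusted ANOVA model".
- SAP 7.6 has a general sentence: "Where appropriate, analyses will be stratified based upon a subset of stratification parameters used for randomization". The subset is TTR mutation and 6-MWD split at 325 m.

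Baseline walk distance is collected and defined in SAP 6.1: "For 6-MWD, baseline will be defined as the latest value prior to the first dose".

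**The concern.** An ANCOVA whose only covariate is the treatment group is an ANOVA, or a two-sample t-test, on change scores. The SAP marks its other unadjusted model as unadjusted and gives a reason for it. Here it does neither, which suggests that covariates were left out by oversight.

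Three things follow.

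1. **Interpretation.** Sensitivity #2 exists to show what missing data do to the result. The natural comparator is the MMRM, the only other modelled comparison of 6-MWD in meters. The two differ in the patients and visits used and also in the covariates, so the effect of missing data is mixed with the effect of adjustment.
2. **Imbalance.** Completers are selected after randomization, so baseline balance is not protected. The plan expects more deaths on placebo (20% against 13%), and protocol 1.4 treats 6-MWD as prognostic. Placebo completers could therefore start from a somewhat higher baseline. A change score subtracts baseline but does not remove the correlation between baseline and change.
3. **Precision.** If baseline predicts change, leaving it out widens the interval.

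**Working it through.** **The plan's own figure.** SAP 2.3 gives N = 120 and 60, an effect of 0.55 SD, SD 70 m, deaths of 13% and 20%, two-sided 0.05 and about 90% power.

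- Effect: 0.55 × 70 = 38.5 m, stated as 39 m.
- Enrolment: 180 / (1 − 0.10) = 200.
- An unstratified Finkelstein-Schoenfeld simulation (6,000 trials per setting, exponential deaths, normal change, permutation variance) gives 88.7% power. It gives 89.2% with an effect of 39/70 SD and 89.9% with a hazard ratio of exactly 0.6. Simulated type I error is 4.7%.

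The planning inputs are therefore coherent and can be reused. The documents state no precision for Sensitivity #2 itself.

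**Completers (assumed).** 120 × 0.87 = 104.4 and 60 × 0.80 = 48. Starting from 200 enrolled gives the same: 133 × 0.87 × 0.90 ≈ 104 and 67 × 0.80 × 0.90 ≈ 48. Patients who are alive but have no Month 18 walk would lower these counts.

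**Treatment-only model.** SE = 70 × √(1/104.4 + 1/48) = 12.2 m. Half-width = 1.96 × 12.2 = 23.9 m. Power for 38.5 m is Φ(38.5/12.2 − 1.96) ≈ 88%.

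**With baseline added.** The SE is multiplied by √(1 − r²), where r is the within-arm correlation of baseline with change. The exact version also multiplies by √((N − 2)/(N − 3)) for the degree of freedom used, with N = 152. The documents give no r, so a range is shown.

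| Assumed \|r\| | Half-width, simple (m) | Half-width, with df term (m) | Power for 38.5 m, with df term |
|---|---|---|---|
| none (treatment only) | 23.9 | n/a | 88% |
| 0.1 | 23.8 | 23.9 | 88% |
| 0.2 | 23.4 | 23.5 | 89% |
| 0.3 | 22.8 | 22.9 | 91% |
| 0.5 | 20.7 | 20.8 | 95% |

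The reduction is about 2% at 0.2, 4 to 5% at 0.3 and 13% at 0.5.

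As a guide to r, suppose baseline and Month 18 distances have equal SDs and correlation ρ. Then |r| = √((1 − ρ)/2). For ρ from 0.5 to 0.9 (assumed), |r| runs from 0.50 down to 0.22, and the SE falls by about 13% down to 2.5%.

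**Imbalance.** The unadjusted difference shifts by the baseline gap times the slope of change on baseline. With an assumed slope of −0.3 and assumed gaps of 10 and 20 m, the shift is 3 and 6 m, or 8% and 15% of the 39 m design effect. With a negative slope and placebo completers starting higher, the shift favors revusiran. Nothing in the documents fixes the gap, the slope or its sign; this shows scale only.

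**The case against.** The strongest reply is that little depends on this model. The MMRM already gives a baseline-adjusted Month 18 difference in meters with its interval. Under SAP 7.6.1, efficacy rests on the primary analysis of each co-primary endpoint, and no robustness rule is tied to Sensitivity #2. The precision gain is small unless r is well above 0.3. All of this stands, and it makes the point a minor one. It does not explain why the complete-case model should drop covariates that its counterpart for TTR keeps.

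A reader might also infer stronger things that the documents do not support:

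- **That the analysis ignores baseline walk distance.** The outcome is a change score, so baseline is subtracted for every patient. What is missing is baseline as a covariate.
- **That it ignores the stratified randomization.** The general sentence in SAP 7.6 allows stratification where appropriate. The SAP calls the descriptive analyses that follow unstratified but does not say this of Sensitivity #2. The text is ambiguous. Even on the generous reading, it would add only TTR mutation and 6-MWD split at 325 m, not continuous baseline.
- **That adjustment would repair the complete-case set.** It corrects observed imbalance in the covariates used. Selection by death or lost walking ability remains. Nor is the set exactly those who kept their ability: Appendix I counts a patient needing a new walking aid or more oxygen as having lost it, and the SAP does not say that such a distance is set to missing.
- **That a wide interval here would make the trial look fragile.** At |r| of 0.2 to 0.3, power moves only from 88% to 89 to 91%.

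**Conclusion.** The point holds as a low-cost improvement to a sensitivity analysis. As written, Sensitivity #2 is an unadjusted comparison labelled ANCOVA. It is out of line with the MMRM and with the TTR complete-case analysis. The main consequence is interpretive: a gap between it and the MMRM could come from the missing-data handling, the covariates or both. Uncorrected baseline imbalance among completers is second.

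The loss of precision comes third: a half-width of 23.9 m against about 23.4 to 20.7 m. That rests on SD 70 m, about 104 and 48 completers, and an assumed correlation of 0.2 to 0.5. At 0.1 or less there is practically no gain. The primary joint rank test, its power and the success criterion do not change.

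**What to change.** Define Sensitivity #2 as an ANCOVA of Month 18 change in 6-MWD with treatment, continuous baseline 6-MWD (as defined in SAP 6.1) and TTR mutation. Report the adjusted treatment difference with its 95% CI.

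This brings the model into line with the MMRM covariates, so a comparison of the two speaks mainly to missing data. The MMRM also names screening 6-MWD. That term can be carried over if an exact match is wanted, although continuous baseline covers much of the same information. NYHA class need not be added: it is outside the stratification subset in SAP 7.6 and is not among the terms named in the MMRM, so including it would create a new mismatch.

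If an unadjusted comparison is intended, call it an unadjusted ANOVA and state why.

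The cost is one line of SAP text and a couple of degrees of freedom. The variables are already collected.

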7.6.1.3 Percent reduction in serum TTR from Baseline over 18 months

The primary analysis for the co-primary endpoint of percent change in TTR from baseline over 18 months will be analyzed using an Analysis of Covariance (ANCOVA) model.

The dependent variable used in the ANCOVA model w	rill be area under the effect curve (eAUC) to			
quantify the percent reduction in TTR from baseline over 18 months. The covariates used in the model				
will be treatment group, TTR mutation	and 6-MWD at Screening			
and baseline TTR serum levels. The	difference in the adjusted mean eAUC between			
treatment groups will also be presented with associated 95% confidence interval. The dependent variable				
will be log transformed.	-			

Calculation of eAUC will be based on trapezoidal method, where the y-axis is percent reduction in serum TTR and the x-axis is time since first dose of study drug. Assessments missing due to death or discontinuation will be imputed using the baseline value, and thus the percent change will be 0%. The span of time will start at time 0 (baseline) and end at month 18. Only scheduled visits will be included in the calculation of eAUC.

7.6.1.4 Sensitivity Analyses for Percent Reduction in Serum TTR from Baseline over 18 months

Sensitivity #1: Address impact of baseline factors

The eAUC will be analyzed using an unadjusted ANOVA model. The covariates of the model will be treatment group and the dependent variable will be eAUC.

Sensitivity #2: Address robustness using a different distributional assumptions

A mixed-effects model repeated	l measures (MMRM) ana	alysis based on the re	stricted maximum likelihood
(REML) method for estimation w	vill be performed for rela	tive fold change in s	serum TTR. The dependent
variable will be relative fold cha	ange defined as (TTR va	lue at follow-up visi	t/baseline TTR value). The
covariates used in the model wil	ll be treatment group, vis	sit, treatment group b	by visit interaction, TTR
mutation	and 6-MWD at Screeni	ng	and baseline
TTR serum levels. The difference	ce in the adjusted mean i	relative fold change	n serum TTR between
treatment groups and associated	95% will also be presen	ited. The dependent	variable will be log
transformed.			

Sensitivity #3: Address influence of missing data

Complete Cases (CC) analysis will include all patients with non-missing TTR results at month 18. The mixed-effect model used in the sensitivity #2 will be employed. No imputation will be considered. The dependent variable will be log transformed.

Below are additional descriptive analyses of serum TTR. These analyses will be unstratifed using the mITT population.

Serum TTR: Descriptive statistics of serum TTR values, change from baseline in serum TTR values and percent reduction in TTR values will be presented for each treatment group. An additional summary table of descriptive statistics for the maximum percentage reduction in TTR for each treatment group will also be presented.

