9.2.3. Efficacy Analyses

9.2.3.1. Primary Efficacy Endpoint

There are two co-primary endpoints. The first co-primary endpoint is change from baseline (in meters) for a 6-MWD conducted 18 months after randomization. The primary efficacy analysis for the comparison of 6-MWD between treatment groups will be conducted using Wilcoxon Mann Whitney-based test statistics that will take into account informative missingness due to death and the loss of the ability to perform the test. Briefly, in this stratified non-parametric rank sum analysis, all pairs of patients within a stratum are compared. A pair of patients is compared first on time to death (if death occurs before 18 months); second on time until the inability to perform the test (if it cannot be determined as to which patient in a pair lived longer); and third on the change from baseline in 6-MWD at the time of the last assessment shared by both patients (if it cannot be determined as to which patient in a pair lived longer and which retained the ability to perform the 6-MWD longer). The analysis will be stratified based on the stratification parameters that are used for randomization.

The second co-primary endpoint is percent reduction from baseline in serum TTR using enzyme-linked immunosorbent assay. The area under the effect curve (eAUC) for percent reduction from baseline in serum TTR over time, where the y-axis is percent reduction and the x-axis is time since randomization, will be compared across groups using Analysis of Covariance (ANCOVA), in which the stratification variables and baseline serum TTR level will be included in the model as covariates. The eAUC will be computed using the trapezoidal method, where assessments missing due to death or discontinuation will be imputed using the baseline level, i.e., the percent reduction will be assumed to be 0%.

The study will have demonstrated efficacy if the p-value for each of the co-primary endpoints is \leq 0.05 (2-sided).

Sensitivity analyses for each co-primary endpoints, including different methods for handling of the missing data, will assess the robustness of the primary analysis for the mITT population.

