2.3 Sample Size and Power

For the 6-MWD primary endpoint, a sample size of 180 with a 2:1 treatment allocation (N=120 on revusiran and N=60 on placebo) has approximately 90% power to detect a treatment difference of 0.55 standard deviations using a Finkelstein and Schoenfeld analysis with a two-sided significance level of 0.05. This assumes that 20% of placebo patients and 13% of revusiran patients will die before the 18 month assessment (ie, hazard ratio = 0.6). Assuming a standard deviation of 70 meters in change from baseline, this would correspond to approximately 90% power to detect a treatment effect of 39 meters in the 6-MWD. Assuming a 10% patient dropout rate, approximately 200 patients will be enrolled in the study. Note that power for the comparison of percent reduction in serum TTR between treatment groups is expected to be >90% for a significance level of 0.05; sustained knockdown of serum TTR levels

>85% has been observed in healthy volunteers and patients receiving revusiran. For this reason, the overall power to establish efficacy is expected to be approximately 90% under the assumptions described above.

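### The serum TTR co-primary is planned as an equal-variance ANCOVA, but 0% imputation makes untransformed eAUC more variable on revusiran, so its 95% CI is too wide, and the SAP's log transformation does not cure this

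*SAP*

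**What the plan says.** Under SAP 7.6.1.3 the eAUC for percent reduction in serum TTR over 18 months "will be analyzed using an Analysis of Covariance (ANCOVA) model". The terms are treatment, TTR mutation, 6-MWD at Screening and baseline TTR. The difference in adjusted means between "treatment groups will also be presented with associated 95% confidence interval".

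For assessments missing because of death or discontinuation, the SAP says that "discontinuation will be imputed using the baseline value, and thus the percent change will be 0"%. Protocol 9.2.3.1 has the same rule: "the percent reduction will be assumed to be 0"%.

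The SAP adds that the dependent variable "will be log transformed". Protocol 9.2.3.1 names no transformation. Neither document specifies unequal variances or a robust standard error for this endpoint. The SAP does name a sandwich estimate for recurrent hospitalizations (7.6.2.5 and 7.6.3.10). TTR sensitivity analysis #1 (SAP 7.6.1.4) is an unadjusted ANOVA of eAUC, with no log stated.

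The decision rule is in SAP 7.6.1: "Efficacy of revusiran will be established if the p-value (2-sided) is" at most 0.05 for each co-primary endpoint.

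**The concern.** A standard ANCOVA uses one residual variance for both arms. The plan's own inputs work against that. Most revusiran patients should sit near 85% reduction, so setting the missing visits of a patient who dies or drops out to 0% moves that patient's eAUC a long way. A placebo patient is already near 0% and barely moves. The revusiran arm therefore gains spread that the placebo arm does not. It is also twice as large, so it dominates the pooled variance.

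What is at stake is the reported precision of a co-primary effect. The adjusted mean difference with its 95% CI is the planned estimate of TTR lowering, and it should have the coverage it claims. The unadjusted ANOVA pools the variance in the same way, so it would not reveal the problem.

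**Working it through.** **Inputs from the documents** (SAP 2.3; visits from Protocol Table 1-1)
- Allocation 2:1 of about 200 patients: 200 × 2/3 ≈ 133 and 67.
- Knockdown above 85%; 85% is used.
- Deaths: "20% of placebo patients and 13% of revusiran patients will die before the 18 month assessment".
- Dropout 10%, taken as equal in the two arms.
- TTR at months 0, 1, 2, 3, 6, 9, 12, 15 and 18; trapezoidal rule; 0% after death or dropout.

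**Assumptions, because the documents give no figure**
- Between-patient SD of knockdown 5 points.
- TTR measurement CV 5% to 20%, log-normal.
- Exponential times to death and dropout.
- One pre-dose TTR sample; stratification covariates left out of the simulated model.

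**The plan's own figures.** Enrolment is 180/0.90 = 200. The 6-MWD power is planned "using a Finkelstein and Schoenfeld analysis with a two-sided significance level of 0.05". A simulated Finkelstein-Schoenfeld test (120/60, 0.55 SD, deaths 13% and 20%) gives 88.7% against the stated 90% or so. Simulated power for TTR is 100%, consistent with the stated figure above 90%.

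**Does the imputation cause the spread?** With no deaths or dropout, the revusiran SD of eAUC/18 is 4.9 to 6.1 points. With the planned attrition it is about 22. It does.

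**Size in percentage points.** Take 2m patients on revusiran (SD s_r) and m on placebo (SD s_p).
- Pooled SE² = [(2s_r² + s_p²)/3] × [1/(2m) + 1/m] = (2s_r² + s_p²)/(2m).
- Correct SE² = s_r²/(2m) + s_p²/m = (s_r² + 2s_p²)/(2m).
- Ratio of pooled to correct SE = √[(2s_r² + s_p²)/(s_r² + 2s_p²)].

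For s_r = 22 and s_p = 9.5: √[(968 + 90.25)/(484 + 180.5)] = √1.593 = 1.26. As s_p approaches 0 the ratio approaches √2 = 1.41, the ceiling in this formula; coverage there is about 99.4%.

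| TTR CV | Placebo SD | SD ratio | SE ratio, formula | SE ratio, simulated ANCOVA | Coverage of 95% CI | Half-width, pooled → HC3 |
|---|---|---|---|---|---|---|
| 5% | 4.7 | 4.7 | 1.37 | 1.36 | 99.0% | 5.3 → 3.9 |
| 10% | 9.5 | 2.3 | 1.26 | 1.25 | 98.3% | 5.5 → 4.4 |
| 15% | 14.5 | 1.5 | 1.14 | 1.13 | 97.3% | 5.8 → 5.0 |
| 20% | 19.7 | 1.1 | 1.04 | 1.07 | 96.6% | 6.2 → 5.8 |

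The formula leaves out the baseline TTR covariate, which the simulated ANCOVA includes. HC3 coverage is 94.7% to 95.7%. A second simulation on the same inputs gave a pooled SE 15% to 41% too large and coverage of 97.7% to 99.1%.

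**Effect on the decision.** The difference is about 73 to 76 points with an SE near 3, so the test statistic is above 20. With no drug effect on TTR and equal attrition the arm variances are equal, and simulated type I error is 5.5%.

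**Log scale, as the SAP states.** eAUC is zero or negative in 52% to 54% of placebo patients and about 1.4% of revusiran patients, and its log is then undefined. Among positive values the SD of log eAUC is about 0.52 on revusiran and 1.2 on placebo, so the ordering reverses. If the undefined values are dropped, the pooled SE is about 0.63 of the correct one and coverage is about 78%; HC3 gives 93% to 94%.

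**The case against.** The strongest objection is that an argument in percentage points addresses an analysis the SAP does not plan, because the SAP takes logs. On the log scale, neither the direction nor the existence of the error is settled until the SAP says what happens to values at or below zero. With log(eAUC/18 + c) for c from 10 to 100, which are assumed rules and not the SAP's, the ratio of pooled to correct SE ran from 0.74 to 1.32, and was 1.01 at c = 50 with CV 10%. This stands. The too-narrow result holds only if undefined values are dropped, and a variance option added to an undefined log repairs nothing. That is why the log must go first. The percentage-point analysis still matters, because the protocol names no transformation and sensitivity analysis #1 states none.

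The size also rests on a placebo SD that the documents do not give. If dropout is varied from 0% to 30% as well, the SD ratio runs from 0.9 to 6.3. This stands too. A reader might infer that revusiran is bound to be far more variable, but at CV 20% the two SDs are nearly equal.

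A reader might also infer that the efficacy test is invalid or the TTR effect overstated. The documents do not support that. Efficacy rests on the p-value, the interval is presented alongside it, and in percentage points the error is conservative.

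Nor does the point reach TTR sensitivity analyses #2 and #3. They model log fold change by visit, the 0% rule is specified only for eAUC, and #3 excludes imputation.

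**Conclusion.** The point holds for the precision of the TTR estimate. In percentage points, under the planned attrition and an assumed TTR CV of 5% to 20%, the pooled standard error is roughly 7% to 41% too large and the 95% CI covers about 97% to 99%. The half-width is 0.4 to 1.4 points too large (6.2 − 5.8 and 5.3 − 3.9) around a difference of 73 to 76 points. The decision at p ≤ 0.05 and the power above 90% are unaffected.

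The SAP's log transformation does not rescue the interval. It is undefined for about half of the placebo arm, and it reverses the imbalance among the rest. The missing rule for values at or below zero is the more serious fault of the two. The sizes depend on the assumed TTR variability and on dropout being equal in the two arms.

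**What to change.** In SAP 7.6.1.3, in this order:
1. Remove the log transformation of eAUC, in line with Protocol 9.2.3.1, and analyse it in percentage points (for example eAUC divided by 18 months).
2. Keep the ANCOVA terms, but state that the test and 95% CI use HC3 standard errors or arm-specific residual variances (for example PROC MIXED with REPEATED / GROUP=treatment and Satterthwaite or Kenward-Roger degrees of freedom).

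Apply the same variance rule to the eAUC ANOVA in TTR sensitivity analysis #1. On this point, leave #2 and #3 as they are.

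The cost is one sentence removed, one added and one option in the SAS code, before unblinding. No new data are needed, and simulated power stays at 100%.
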